	 Coil: Two Cool-B65 Butterfly coils (one connected to the rTMS and one disconnected) Duration: 10 treatment days over a maximum of 21 days beginning on (Randomized Day) RD +1 A temporary barrier is positioned between the participant and the MagVita, preventing the participant from seeing the MagVita Active-assigned group Personalized treatment stimulus rate between 8 and 13 Hz, determined by the participant's EEG intrinsic alpha frequency Sham-assigned group An unconnected coil will be positioned at Fz, with the cable routed through the barrier, so that it appears to be connected. The Connected coil will be kept on the MagVita behind the barrier. In this way, the participant hears the ticking sound of the rTMS emanating from behind the barrier, but no magnetic field is generated by the disconnected coil, so the sham-assigned participant receives no treatment
Study Treatment Regimen: Stage 2 Open Label	 Active eTMS: Personalized treatment stimulus rate between 8 and 13 Hz, determined by the participant's EEG intrinsic alpha frequency Coil location: Fz (midline frontal/prefrontal cortex) Coil: Cool-B65 Butterfly coil Treatment stimulus intensity 50% of motor threshold Dose is 1 study treatment: 5 seconds of repetitive stimulation, with an intertrain interval of 20 seconds, for 15 minutes Doses per treatment day = 2 Minimum rest time from the end of the first dose to the start of the second dose = 30 minutes Duration: 10 treatment days over a maximum of 21 days beginning on day (Open Label Day) OD +1 OD+1 to occur within 2 months of completion of F1 data collection
Schedule of Visits	 Participants evaluated for eligibility via Screening phone call visit (SC). Following SC, a Baseline Visit (BL) will be conducted to gather assessments. All participants will be encouraged to utilize no-cost access to background supportive treatment (BST) made available through the Supportive Treatment Center. Stage 1: Safety Pilot Study: Screening Visit (SC): SDay-28 to SDay-2 Baseline Visit (BL): SDay-28 to SDay -1

	 Begin Active eTMS on SDay +1 Finish Active eTMS between SDay +10 and SDay +21
	 BST from SDay +1 through SDay +21
	 F1 data collection visit after the last eTMS treatment - between
	SDay +10 and SDay +21
	Stage 2: Randomized Controlled Trial
	All participants
	• Screening Visit (SC): RDay-28 to RDay-2
	 Baseline Visit (BL): RDay-28 to RDay -1
	• Randomization: RDay +1 prior to first study treatment
	• Begin Assigned study treatment (Active or Sham) on
	RDay+1

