- 15. Clinically significant medical illness, psychopathology, or other condition, that in the judgment of the Investigator might pose a potential safety risk to the participant or limit the interpretation of study results

Suicidality and Harm to Others

High suicide risk individuals will be ineligible as well as those with clinically significant psychopathology or other psychiatric disorders that may pose a safety threat to the participant. The U.S. Army Medical Command (United States Army Medical Command, 2014) screens individuals discharged from emergency departments and inpatient units. MEDCOM uses the Columbia Suicide Severity Rating Scale (C-SSRS) with triage points. The 6-item scale identifies ascending levels of risk, as subsequent items from 1 to 6 are endorsed as having occurred within the past month. Item 6 is related to actual preparatory activities, and it asks for additional time frame specificity, such as 1 week, 1 month, 3 months, and 1 year.

We will implement a suicide risk reduction plan for individuals found ineligible to participate in eTMS-PTSD-001 by virtue of suicidal ideation above a certain risk level. It is anticipated that some potential participants will have a measure of suicide risk, but these are some of the individuals for whom MeRT should be tested for benefit. It is therefore inappropriate to declare all persons with suicidal ideation ineligible. A triage plan tailored to the eTMS-PTSD-001will be implemented that considers the competing considerations of allowing enrollment of individuals with some measure of suicidal ideation yet excluding individuals at higher levels of risk, who require immediate intervention.

At the BL Visit, potential participants will be administered the C-SSRS. The C-SSRS incorporates findings from suicide literature and has prospective data that validates the scale's ability to identify risk probability ranges for potential future suicidal behaviors. The first 5 items of the scale divides responses according to whether the participant endorses an item within the past month or at a more remote time in the past. Items 1 and 2 refer to passive suicidal ideation

without intent or plan. Item 3 refers to whether a method has been considered, but intent is absent.

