Individuals who endorse items 4 or 5 within the past month, i.e., intent without plan, or intent with plan, respectively, will be ineligible to participate in eTMS-PTSD-001. Item 6, referring to actual preparatory or attempt activities, asks for a time frame for those activities. If an individual endorses item 6 within the past 6 months for preparatory activities that did not constitute an attempt, they also will be ineligible. If the individual endorses item 6 with an attempt occurring at any time in the past, they will be ineligible.

When an individual is found to be ineligible secondary to responses suggesting likelihood of self-harm, or expression of homicidal feelings toward inappropriate targets (e.g., if active military personnel express homicidal feelings toward individuals who are not enemies of the United States), screening will be terminated. All individuals deemed ineligible due to suicidal ideation, whether deemed at imminent risk or not, will be given resource information that explains where resources and assistance may be obtained. Individuals deemed ineligible on the basis of suicide risk or homicidal ideation are permanently ineligible for the trial.

When an individual is screened and meets the exclusion criteria for suicidal risk or expresses inappropriate homicidal intent, the Medical Monitor, Site PI or his/her medically qualified designee will be contacted. If the Medical Monitor, Site PI/designee deems the individual to be at imminent risk, an emergency medical service or the police will be called to transport that individual to the nearest civilian hospital, or to the appropriate military hospital as appropriate to military status. If the individual is not deemed to be at imminent risk, the individual will be advised to call or present to the closest Emergency Department, call 911, or the appropriate crisis hotline.

STUDY TREATMENTS

Equipment

All equipment used to evaluate and treat participants in the trial are either FDA-cleared or are exempt from clearance and listed with FDA. The MagPro family of magnetic stimulators are manufactured by Tonica Electronik, A/S, a sister company of MagVenture. Specific application of the device can be arranged by selection of multiple coil configurations, varied in stimulation area (<1" to >10"), rate (single pulse to <30/sec for the R30 stimulator used in the eTMS-PTSD-001 trial), and output intensity (up to 3.9 tesla) depending on the triggering program and type of coils.

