Each study recruitment site will be assigned a unique identifying code. A unique participant identification number and participant character code identifier will be assigned to every potential participant who gives consent at the Screening Visit and provides any data at the Baseline Visit. Every participant will be uniquely identified by these three identifiers. All identifiers will be recorded on all study data collected. A file linking the study identifiers to the participant's name will be secured at the study site in a locked cabinet in a secure location. The Principal Investigator will receive a copy of the linkage document periodically (e.g., weekly), and will store it in a locked cabinet in a secure location.

To maintain confidentiality, the participant's name will not be recorded on any study document that will be in the participant's study paper files, or on any input to the study electronic database. Any consent forms or paper copies thereof, will be filed separately from other study forms and will not bear the participant's numerical or character identifiers.

The MagVita device input field requirements, and study identifiers will be harmonized. Photographs/avatars or other identifiers will be used as part of the setup screens to ensure that the individualized study treatment protocol calculated for the individual is what the stimulator outputs to the engaged coil to ensure the safety of participants assigned to active eTMS.

Baseline Visit and Eligibility Determination

Potential participants will undergo assessments and EEG recording during a Baseline Visit (BL), which occurs on-site following the Screening Visit (SC). Eligibility is determined after all BL procedures have been conducted, results have been reviewed, and the EEG has been reviewed for neurological and EEG quality exclusionary conditions. A neurologist or neurosurgeon with adequate training and experience in reading EEGs will review EEG quality. If a potential neurological exclusionary condition is noted by Sponsor, i.e., general or focal slowing or ictal spikes, it will be brought to the attention of a medically qualified Investigator or member of the IDE Sponsor's staff, who will be consulted to confirm eligibility status.

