If a potential participant is a female of child-bearing potential (i.e., not 2 years post-menopausal, and not sterile by tubal ligation or hysterectomy), a urine pregnancy test will be conducted. Unless the test is negative, the individual is not eligible to participate. The site Investigator or Clinic Coordinator will provide the result of the test to the potential participant. If the result is positive or indeterminate, the individual will be advised to confirm with a health care provider. A copy of the test package insert will be provided to each individual and the possibility of both false negative and false positive results noted. If it is determined at a later date, after the screening period has expired, that the potential participant is not pregnant, then the screening process can be repeated in totality, and if she is eligible, she may be enrolled.

Eligibility is not confirmed until an eligibility checklist and any supporting materials needed have been reviewed by the site Investigator, and s/he has confirmed, in writing that enrollment may proceed. No participant will be enrolled without such written confirmation.

Continued eligibility related to safety factors will be checked before conducting active eTMS treatment in the open-label extension for those participants who opt-in.

Additional Considerations for Stage 2 Randomized Controlled Trial

Randomization

Participants in Stage 2 will be assigned randomly to one of the two treatment groups (Active eTMS treatment vs Sham eTMS treatment). The treatment allocation will be in a 1:1 ratio, using permuted variable blocks of size 2, 4, and 6.

Participants will be randomized at the beginning of the first treatment visit. This will occur after giving informed consent at SC; after eligibility is determined from data collected at the BL Visit; after all data necessary to determine eligibility is reviewed and documented on the Eligibility data collection form; and **after written confirmation to proceed is provided by the site Investigator**. Participants will be randomized at the last possible moment (just prior to the first treatment) in order to avoid randomizing an eligible potential participant who thereafter changes his or her mind about participation before the first study treatment can be delivered, or who is not well enough to be treated on that occasion.

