MED: The Morphine-Equivalent Dose is a value that represents the potency of an opioid dose relative to morphine. It is intended to be used as a method of tracking changes in opioid use. The assessment is intended for determining daily dosage, and includes 10 different opioids (Codeine, Fentanyl, Hydrocodone, Hydromorphone, Methadone, Morphine, Oxycodone, Oxymorphone, Tapentado, and Tramadol). Measurements are made in milligrams. A conversion factor is used (Von Korff, et al., 2011), and amounts are summed, resulting in a final amount (in milligrams) of morphine the subject ingested. Levels of >120 MED per day increases risks for overdose by 1.98 (Ciesielski, et al., 2016).

OCS: The Opiate Craving Scale is a 5-item self reported assessment that estimates the cravings an individual has for opiate drugs. This scale was adapted for opiates from The Penn Alcohol Craving Scale (PACS) (Flannery, 1999). Each item measures the severity of cravings on a 6 point scale, for a maximum score of 36. The instrument can be modified to measure weekly or daily cravings. In the present study, the daily instrument will be used.

DAST-10: The DAST-10 is a 10-item, self-report instrument to identify problem drug use. One point is scored for each item on the screen, with total score range from 0-10. Administration time is about 10 minutes.

PSQI: The Pittsburgh Sleep Quality Inventory is a self-administered questionnaire developed to discriminate between "good sleepers" and "poor sleepers." The PSQI is the most commonly used screening tool for sleep dysfunction. The instrument assesses sleep quality disturbances over a 1-month time interval. Nineteen individual items generate seven component scores: subjective sleep quality, sleep latency, sleep duration, habitual sleep efficiency, sleep disturbances, use of sleeping medication, and daytime dysfunction. Scores are summed for a global PSQI score. (Buysse, Reynolds III, Monk, Berman, & Kupfer, 1989) (University of Pittsburgh, 2020) Best evidence synthesis shows strong reliability and validity, and moderate structural validity in a variety of sample populations, suggesting that it fulfills its intended utility. (Mollayeva, et al., 2016).

SEQ: The SEQ is a checklist to evaluate for side effects of eTMS therapy. Expected adverse reactions will be prompted for. For each item, individuals are asked to indicate whether they are experiencing the symptom. Response options are: None, Slightly, Moderate, Severe.

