 - $\circ~$ Short-term. Resolves in the first 1-2 days of the rapy.

- No long-term implications.
- Treatment emergent mania/hypomania
 - \circ Sponsor's clinical use history ~5%.
 - Hypomania is much more common than mania. Often a secondary effect to improved symptoms.
 - Short term. Resolves in the first week of therapy.
 - No long-term implications.
- Anxiety/depression
 - Sponsor's clinical use history showed slight anxiety in ~5% of patients generally occurring in patients responding positively to therapy as awareness of their own behavior develops.
 - rTMS: Very rare in general. Observed when stimulation of RPFC and LPFC (Pascual-Leone, Catalá, & Pascual-Leone, Lateralized effect of rapid-rate transcranial magnetic stimulation of the prefrontal cortex on mood, 1996) (George, et al., 1996) which is not used in the present trial.
 - Short term. Resolves within the second week of therapy.
 - No long-term implications.
- Cognitive changes
 - Sponsor's clinical use history ~5% report an alteration to cognition, associated with fatigue following therapy.
 - rTMS: No evidence of long-term adverse effect on cognitive, perceptual, or motor functions in general (Pascual-Leone, et al., 1993) (Wassermann E. M., 1998)
 - Short-term. Resolves in the second week of therapy.
 - No long-term implications.
- Insomnia
 - \circ Sponsor's clinical use history ~3%.
 - Some patients nap following treatment, which disrupts sleep. Some report a shorter period of sleep initially with an early wake up.
 - \circ Short term. Resolves within the first week of therapy.
 - \circ No long-term implications.
- Dizziness
 - \circ Sponsor's clinical use history ~3%.
 - Patients may feel very relaxed during therapy, and experience mild light headedness when standing afterward.
 - Resolves by asking subject to remain seated and stand slowly, or by giving patient water to drink.
 - Short-term. Resolves in the first 1-2 days of therapy.
 - No long-term implications.
- Auditory effects
 - \circ Sponsor's clinical use history ~3%.

- rTMS: Effects on hearing are very rare. Transient rise in auditory threshold or tinnitus in a small number of cases in general (Pascual-Leone, et al., 1992) (Pascual-Leone, et al., 1993) (Loo, et al., 2001) (Boutros, Gueorguieva, & Hoffman, 2002) (Anderson, et al., 2006).

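### The C-SSRS eligibility screen is not repeated on Day 1, so suicidal intent or preparation that arises after Baseline and is neither volunteered nor noticed meets no scheduled check before first treatment

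*Combined protocol and SAP*

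**What the plan says.** Suicidality and Harm to Others sets both the instrument and the rule. "At the BL Visit, potential participants will be administered the C-SSRS". "Individuals who endorse items 4 or 5 within the past month" are ineligible. So is anyone reporting preparatory acts in the past 6 months, or an attempt at any time. The consequence is final: "Individuals deemed ineligible on the basis of suicide risk or homicidal ideation are permanently ineligible for the trial". The same section deliberately leaves room for people with some ideation short of intent.

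On timing, the Synopsis (Schedule of Visits) gives "Baseline Visit (BL): RDay-28 to RDay -1" for Stage 2, and Table 4 gives the matching window for Stage 1. Baseline Visit and Eligibility Determination says "Eligibility is determined after all BL procedures have been conducted". Under Randomization, assignment comes "after eligibility is determined from data collected at the BL Visit", once the site Investigator has confirmed in writing, and just before the first treatment.

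Tables 4 and 5 mark the C-SSRS at BL and F1 in both stages, and also at F2 and F3 in Stage 2. The Day 1 cell is empty. A check that participants remain eligible on safety grounds is stated only for entry to the open-label extension.

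**The concern.** The plan treats recent suicidal intent as a reason not to treat, but the scheduled measurement behind that decision can be up to four weeks old when treatment starts. History found at BL does not lapse, so the issue is confined to new events. Because people with ideation short of intent may be enrolled, someone who endorsed only item 3 at BL need only move to item 4 to cross the exclusion line. If that person says nothing and nobody notices, no scheduled question stands between the change and the first study treatment.

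The protocol makes such a change plausible without quantifying it. The Introduction cites a 6 to 15 times higher risk of a suicide attempt in civilians with PTSD, and expects psychiatric adverse events in psychiatric populations whether or not stimulation is active. Neither is a rate for this interval or this population.

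**Working it through.** The plan states no figure for this interval, so the check is a day count plus a reading of the schedule.

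**Inputs**
- BL window: day -28 to day -1 (Synopsis; Tables 4 and 5).
- Screening (SC) window: day -28 to day -2; BL follows SC.
- First study treatment: day +1.
- Enrolment: 30 in Stage 1. For Stage 2 the Synopsis and Sample Size Considerations give 120; Study Design and Participant Population give 140.

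**BL to Day 1**
- With no day 0, BL on day -k is k days before day +1. For k = 1 to 28 the interval is 1 to 28 days. The documents define no day 0, so this is the natural reading.
- With a day 0 it is k + 1, or 2 to 29 days.
- BL on day -28 requires SC on day -28 too. If SC precedes BL by even one day, the earliest BL is day -27 and the longest interval is 27 days (no day 0).

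**How much of the look-back is unseen**
- Take a month as 30 days (an assumption). With BL on day -28, 28 of the 30 days before Day 1 fall after the only screen. With BL on day -1, 1 of 30 does.

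**What is scheduled on Day 1**
- Tables 4 and 5 mark Braincheck, concomitant treatments and substance use, SEQ/AEs, motor threshold and treatment. Because these rows carry a Day 1 mark, the empty C-SSRS cell is not a lost column.
- PHQ-SADS, which contains the depression scale, is at BL and F1 only.
- The Introduction describes a check before each treatment covering vital signs, health status, adverse events, sleep loss, alcohol and medication changes. Suicidality is not named.
- Of the SEQ the plan says "Expected adverse reactions will be prompted for". The anticipated effects include "Anxiety/depression" and mania or hypomania, so it may prompt for mood change. Its items are not in the documents, and it is described as a checklist of treatment side effects.

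**Burden of one extra form**
- Interviews: 30 + 120 = 150, or 30 + 140 = 170.
- The documents give no C-SSRS administration time. At an assumed 5 to 10 minutes: 150 × 5 / 60 = 12.5 hours, up to 170 × 10 / 60 = 28.3 hours, over the whole trial.

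**The case against.** The strongest reply is that the interval is already under surveillance:
- Adverse-event reporting starts at BL and covers volunteered complaints and conditions that appear or worsen after screening. An attempt that was life-threatening or led to hospital admission would be an SAE.
- Exclusion criteria 13 (elevated risk) and 15 (Investigator judgment) are worded without reference to the C-SSRS.
- Randomisation waits until the last moment, partly so that someone not well enough is not randomised. Staff are trained to recognise ideation and escalate it.
- The trial-specific triage plan and the Manual of Procedures are outside the documents and might already require a Day 1 check.

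Most of this stands, and it narrows the gap: an event that is reported or noticed would be caught. It does not close the gap, because none of these safeguards is stated to ask about suicidality before first treatment. Recognition also has limits in Stage 2, where the Blinding section describes reduced technician contact and barrier separation.

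A reader might infer more than the documents support:
- *That nobody watches for suicidality between BL and F1.* The safeguards above contradict this. The gap is in scheduled measurement only.
- *That the gap is really 48 days.* BL on day -28 to F1 on day +21 is 28 + 21 - 1 = 48 days (49 with a day 0). Up to 20 of those days are the treatment course, which is a separate matter that a Day 1 form does not address.
- *That stimulation makes the omission dangerous.* The rTMS trials tabulated in the Introduction do not suggest that psychiatric events follow active stimulation, though they concern depression and schizophrenia.
- *That some participants would receive any magnetic pulse unscreened.* Motor-threshold testing is placed at BL in one section and on Day 1 in the tables, so the relevant event is the first study treatment.

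**Conclusion.** The point holds as a modest safety tightening. The measure that decides the suicidality exclusion is scheduled once before treatment, 1 to 28 days ahead of Day 1 (2 to 29 if a day 0 exists), and the tables show no repeat when treatment starts. The exposed group is limited to people with a clean BL screen who then develop intent or take preparatory steps, and in whom this is neither volunteered nor noticed.

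The size of that group cannot be estimated: the documents give no rate of new intent after a clean screen and no distribution of BL timing. The longest interval is an edge case.

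The conclusion rests on the schedule tables being complete. If the Manual of Procedures already requires a Day 1 check, only the tables need correcting. It would also be wrong to infer that efficacy results are affected: the gap falls before assignment and applies alike to both arms, so the Stage 2 comparison is not biased.

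**What to change.** Add a C-SSRS to the Day 1 column of Tables 4 and 5, with the recall period written out as since BL. The abbreviation list names a follow-up version, but the documents do not describe its recall period, so the protocol should state it. Have the staff who give it at BL give it again, before randomisation in Stage 2 and before first treatment in Stage 1. Apply the existing criteria as of that date; no new threshold is needed. BL is at most 28 (29) days earlier, so intent since BL falls within a 30-day month, preparatory acts fall within 6 months, and an attempt counts at any time. Use the existing referral path for anyone who meets them. If the Manual of Procedures already requires this check, show it in the tables.

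The cost is one cell in each of two tables and 150 to 170 interviews, or 12.5 to 28.3 staff hours at the assumed 5 to 10 minutes. Day 1 already repeats Braincheck, which averages 15 minutes. A few late screen failures are possible, and under the current rule they would be permanent, in a trial that deliberately keeps some people with ideation. Because the form precedes randomisation, it removes nobody from the ITT population.
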